STUDY PROTOCOL

Title: Endocardial ablation of ganglionic plexuses versus pacemaker implantation in patients with symptomatic sinus node dysfunction (DIS NERVA-PACE study).

Protocol code: 2021/307

Sponsor: Hospital Universitario Clínico Universitario de Santiago

Date of the document: 17/10/2021

Project background and rationale

Symptomatic sinus node dysfunction (SND) comprises a series of symptoms attributable to incapacity of the sinus node (SN) to conduct or generate stimuli, and therefore to generate a heart rate adapted to the needs of the individual⁽¹⁾. According to the latest report of the Spanish Pacemaker Registry, sinus node dysfunction (SND), or sick sinus syndrome, was the second most common cause of pacemaker implantation, after atrioventricular block (AVB), representing 28.4% of all implantations—with bradycardia-tachycardia syndrome being the most common disorder in this subgroup (5.9%), followed by sinus bradycardia (5.1%)⁽²⁾. Although the main cause of SND is considered to be intrinsic due to idiopathic progressive fibrosis of the conduction system related to patient age, SND can also be of extrinsic origin due to dysfunction of the autonomic nervous system secondary to an excessive increase in vagal tone⁽³⁾. In some cases, however, it may be attributable to the coexistence of both conditions, i.e., SND overlying an accentuated parasympathetic tone (particularly in younger patients with paroxysmal episodes).

For over 20 years, the autonomic nervous system (ANS) has been known to influence the development of both ventricular and supraventricular arrhythmias, and the appearance of disorders in conduction of the cardiac rhythm⁽⁴⁾. The ANS is composed of both the parasympathetic nervous system and the sympathetic nervous system, organized into a complex structure of three interconnected levels: a first cerebral level, a second spinal cord level, and a third cardiac level. The latter level in turn is composed of the ganglionic plexuses located at epicardial level. From the anatomical perspective, these plexuses comprise the right anterior ganglionic plexus, the left upper ganglionic plexus, and the left and right lower ganglionic plexus. One way of assessing the contribution of the anatomical component in cardiac impulse conduction is the atropine test: a positive or normal response (defined as an increase in frequency > 25% or > 90 bpm after atropine infusion according to some studies) could be associated to a greater autonomic dysfunction component in these patients and to a lesser intrinsic component⁽⁵⁾. According to the latest European clinical guides, patients presenting SSS with clinical and electrocardiographic correlation are candidates for cardiac pacing (level of recommendation IB), which has been shown to improve the symptoms without modifying survival⁽⁶⁾. However, despite pacemaker implantation, the recurrence of syncope has been reported in up to 17.5% of all cases at 5 years in this patient population, in some series⁽⁷⁾. This may be due to the frequent association between SSS and a neurally mediated or reflex mechanism.

For over a decade and after the confirmation of effective denervation in experimental models in dogs, there have been reports of endocardial radiofrequency ablation of the ganglionic plexus (GP) in the treatment of patients with neurally mediated syncope, SND or functional AVB - even as an alternative to permanent pacemaker implantation. This percutaneous technique, also known as cardiac neuromodulation, involves the location and subsequent radiofrequency ablation of the atrial epicardial parasympathetic ganglia through high-frequency stimulation in search of vagal responses, the presence of fractionated electrograms, or an empirical anatomical approach⁽⁸⁾. The final objective of parasympathetic denervation is to induce vagal reflex attenuation, thereby preventing cardioinhibition in these patients. The evidence on this technique is mainly focused on the treatment of neurally mediated syncope. In patients (n = 43) with neurally mediated recurrent syncope and a normal atropine test result, Pachon et al. found that after left and right endocardial denervation, only 6.9% of the patients showed recurrence of syncope (in two-thirds with a vasodepressor profile) over a mean follow-up of 45 months⁽⁹⁾. On the other hand, Debruyne et al., in a series of 20 patients with syncope and a positive tilt test or SSS and sinus pause > 3 sec, recorded a 95% decrease in the frequency of syncopal episodes at 6 months of follow-up, performing single denervation of the right anterior ganglionic plexus (RAGP) through a strictly right-side approach with ablation on the posteroseptal side of the junction between the superior vena cava and the right atrium⁽¹⁰⁾. In the group with SSS (n = 8), only one patient presented recurrence of syncope with a pause > 3 sec, and required pacemaker implantation. These results coincide with those obtained in a series of 115 patients with neurally mediated

syncope, in which ablation of the RAGP was the procedure most associated to an increase in heart rate, and where after 18 months a total of 92.2% of the patients had not presented recurrence of syncope (11). Lastly, the largest series in patients with SSS was published by Qin et al.⁽¹²⁾. These authors performed endocardial ablation of the four main left GP and of the plexus located between the aorta and the superior vena cava in 62 patients with symptomatic sinus bradycardia, achieving an increase in mean heart rate that proved less manifest in the group of patients > 50 years of age (n = 22). Despite this, only 13.6% of the patients in this subgroup required pacemaker implantation after 12 months—with no pacemaker implantation being needed in those under 50 years of age. At present, our center performs this intervention in patients with such characteristics, with good outcomes, and having avoided pacemaker implantation in 7 patients.

Scientific and practical interest of the project

Although this is a promising technique, no randomized studies have warranted its use in functional SSS. Furthermore, no solid long-term data are available, and most of the studies carried out to date involve heterogeneous groups of patients. At present, there is a randomized trial in the recruitment phase (NCT04149886) that will randomize patients to cardiac neuroablation followed by pacemaker versus direct pacemaker implantation, in which the primary endpoint will be percentage atrial stimulation. However, this trial will not contribute data on the safety of the strategy or any conclusions from the clinical perspective. Consequently, at this time, its usefulness in the context of more elderly patients—which are traditionally the subjects excluded from studies of this kind—is not known.

On the other hand, although pacemaker implantation is firmly indicated in the context of SND, it only affords symptomatic benefits, with no impact upon survival, and moreover has a non-negligible incidence of complications—particularly problems related to infection associated with the device. The fact that a technique is available, described as safe according to the published series and able to reduce the recurrences of syncope in certain groups of patients with associated autonomic dysfunction could modify the therapeutic algorithm—avoiding permanent pacemaker implantation from the start and thus obviating unnecessary ventricular pacing.

References:

To assess differences in the improvement of quality of life at 6 months in both groups and between the two groups. The SF-36 health questionnaire will be used to evaluate symptoms. This is a widely validated instrument comprising 36 items or questions that address aspects referred to perceived health: physical function, physical role, bodily pain, general health, vitality, social function, emotional role and mental health. In addition, the questionnaire includes an item that evaluated the change in health condition versus the previous year. The SF-36 offers the advantages of being easy and rapid to complete, and simple to evaluate. Each health dimension or scale is scored from 0 (most negative perception) to 100 (most positive perception).

Secondary objectives:

- Pacemaker-free survival in the cardiac neuroablation group at 6 months.
- Differences in the recurrence of syncope and syncope-free survival at 6 months between the two groups.
- Change in maximal heart rate and chronotropic incompetence in the exercise test
- Differences in safety (complications) between the two procedures.

Material and methods:

1) Study design

A randomized, open-label multi-center clinical trial is proposed, coordinated by the Electrophysiology Unit of Hospital Clínico Universitario de Santiago (HCUS)(Spain). The study will include patients with syncope symptomatic SND and atropine test positivity, contrasting direct permanent pacemaker implantation from the start versus a ganglionic plexus ablation strategy, in terms of the improvement of symptoms and the recurrence of syncope at one year. Prior to inclusion in the study, all patients will undergo an electrocardiographic study, echocardiography, an atropine test, and a 6-minute walking test.

Treatment groups:

- Intervention group: Endocardial ablation of the ganglionic plexus (cardiac neuroablation).
- Control group: Dual chamber pacemaker implantation without cardiac neuroablation. Pacing programmed in AAIR-DDDR mode.

2) Study setting

The study will be carried out as proprietary research of the Electrophysiology Unit of Hospital Clínico Universitario de Santiago (HCUS). This will be a single-center study, and will be carried out in patients pertaining to this basic healthcare zone.

3) Patient selection and withdrawal

*Inclusion criteria:

- Patients over 40 and under 80 years of age.
- Syncope symptomatic SSS (at least one syncopal episode in the last year) with electrocardiographic evidence (sinus pause > 3 sec, sinus bradycardia with heart rate < 40 bpm, sinoatrial block or chronotropic incompetence in the exercise test).

*Exclusion criteria:

- Relevant structural heart disease (left ventricular ejection fraction < 50%, severe valve disease, hypertrophic cardiomyopathy, previous ischemic heart disease).

- Advanced atrioventricular conduction disorders (second-degree AVB [Mobitz II], complete AVB, advanced AVB).
- QRS interval >130 ms
- A mean life expectancy of less than 12 months.

*Therapeutic failure: in the cardiac neuroablation group, this is defined as the recurrence of syncope at one year. Failure of the procedure is defined as the impossibility of achieving adequate denervation, with a persistently positive atropine test.

*Study withdrawal criteria:

- Syncope secondary to SND registered with electrocardiographic evidence. These patients will be offered pacemaker implantation.
- Impossibility of achieving adequate denervation in the cardiac neuroablation group. In these cases, dual chamber pacemaker implantation will be indicated.

4) *Patient recruitment*

Recruitment will be made of consecutive patients admitted due to syncope secondary to SND in the Department of Cardiology or referred for outpatient pacemaker implantation due to symptomatic SND. The patients who meet the baseline inclusion criteria will be invited to participate in the study, with the selection of those presenting a positive atropine test result.

5) *Sample size*

The estimate sample size is 20 patients in each treatment arm.

6) *Study period*

The study will comprise a follow-up period and will have a duration of one year from the time of the intervention (pacemaker or endocardial ablation). During this year all the complementary tests and necessary clinical follow-up will be carried out. In total, from the presentation of this project, the estimated duration is two years.

7) *Randomization procedure*

Randomization will be performed independently using the OxMar (Oxford Minimization and Randomization) application. This is an open-access minimization and randomization application for clinical studies that operates online in a web setting. After adapting it to our study and following the design of a form, on entering the patient code the program performs minimization or simple randomization correcting for different variables. In our study, we will use sample randomization without stratification for any variable.

8) *Measurements and interventions (primary and secondary endpoints)*

*Primary endpoint:

- Differences in the improvement of quality of life between the two groups at 6 months. As commented above, this will be based on the SF-36 questionnaire, involving a numerical score of 0–100 for each of its 8 scales. The score obtained before the intervention will be compared with that recorded in the last year in both groups for each scale and as regards the total sum. In addition, to evaluate the difference in the improvement of quality of life, comparison will be made of the difference in the score at baseline and after one year between the two groups for each scale and as regards the total sum.

*Secondary endpoints:

- Pacemaker-free survival in the cardiac neuroablation group at 6 months. This will be based on clinical follow-up of the recruited patients.
- Differences in the recurrence of syncope and syncope-free survival at 6 months between the two groups. Comparison will be made of the number of syncopal episodes between both groups per patient and at one year. On the other hand, syncope-free survival will be analyzed. All this will be based on the clinical follow-up.
- Differences in baseline and 6 months exercise test between the two groups.

- Serious complications due to the procedure: in the cardiac neuroablation group, complications will be defined as cardiac tamponade, stroke, the need for urgent surgery and major vascular problems (fistula, aneurysm, bleeding requiring blood product transfusion). In the pacemaker group, complications will be defined as device-related infection, pneumothorax and hemothorax.

9) *Description of the intervention, test to be performed and program of visits*

*Description of the cardiac neuroablation technique: After obtaining informed consent and explaining the risks of the procedure, the patients randomized to the cardiac neuroablation group will undergo the technique under mild sedation. We first will measure the baseline AH and HV intervals, as well as the corrected sinus node recovery time after atrial pacing. Electro-anatomical mapping will be performed (Biosense Webster, USA) using a multipolar catheter both in the right atrium (RA) and in the left atrium (LA) following trans-septal puncture. The ganglionic plexus will be located in a hybrid manner: anatomical (RAGP, left upper GP, right lower GP, left lower GP) and searching for vagal responses after high-frequency pacing (bursts of 10 s, 20 Hz at 25 mA/1 ms duration) in the previously described anatomical zones with an ablation catheter. A new atropine test will be performed after the procedure, with adequate denervation being confirmed if the test proves negative. The patients in this group will remain admitted under continuous monitoring for at least 48 hours.

*Description of the pacemaker implantation technique: After obtaining informed consent and under local anesthesia in the left infraclavicular zone, the subclavian vein will be cannulated, with the insertion of two electrodes: one in the right atrium and the other in the right ventricle. They will be connected to the pacemaker generator, and the surgical wound will be closed. Programming will be made in AAI-DDDR mode. These patients can be discharged after 24 hours with no need for monitoring.

*Clinical follow-up: Clinical follow-up will be carried out at one, three, 6 and 12 months. Follow-up may be performed by telephone. The presence of symptoms and recurrence of syncope will be assessed over follow-up. The SF-36 quality of life questionnaire will be administered at 6 and 12 months.

*Confirmation of adequate denervation: The atropine test will be repeated after 6 months in the cardiac neuroablation group.

*Functional class assessment: The exercise test will be performed in both groups at 6 months.

*Electrocardiographic monitoring and follow-up of conduction disorders: Twenty-four hour Holter monitoring will be made at 2, 6 and 12 months in the cardiac neuroablation group. The patients with implantation of a dual chamber pacemaker will undergo interrogation of the device after 6 months and one year, with special attention to the evaluation of percentage atrial and ventricular pacing.

*Program of visits:

A) Cardiac neuroablation group:

- Month 1: Face-to-face visit for the atropine test, followed by 24-hour Holter monitoring.
- Month 3: Clinical follow-up via telephone.
- Month 6: Face-to-face visit for 24-hour Holter monitoring, exercise test, SF-36 questionnaire and clinical follow-up.
- Month 12: Face-to-face visit for 24-hour Holter monitoring, SF-36 questionnaire and clinical follow-up.

B) Pacemaker group:

- Month 1: Clinical follow-up via telephone.
- Month 3: Clinical follow-up via telephone.
- Month 6: Face-to-face visit for 6-minute walking test, SF-36 questionnaire, clinical follow-up, and interrogation of the device.
- Month 12: Face-to-face visit for 6-minute walking test, SF-36 questionnaire, clinical follow-up, and interrogation of the device.

10) *Timetable and planned study ending date. Distribution of tasks.*

*Timetable and phases of the project:

- Phase 1 (months 1 and 2): Development of the protocol and approval of the study by the local Ethics Committee. Preparation of all the documentation required for registry of the study with the

Spanish Agency for Medicinal Products and Medical Devices (AEMPS). Contact with the SCREN platform for trial monitoring and counseling. Following validation by the AEMPS, registry of the study with the Spanish Clinical Trials Network (REEC) and clinicaltrials.gov.

- Phase 2 (8–10 months): Recruitment and randomization of consecutive patients at Hospital Clínico Universitario de Santiago.
- Phase 3 (12 months): Clinical follow-up of the included patients.
- Phase 4 (1 month): Analysis of results.
- Phase 5 (2 month): Diffusion and publication of results.

Estimated study ending date: from the start of recruitment, the estimated duration of the study is two years.

*Distribution of tasks:

- Protocol design and preparation of the required documentation : [name]/[name]
- Patient recruitment: Department of Cardiology, HCUS.
- Pacemaker implantation: Electrophysiology Unit, HCUS.
- Endocardial ablation of ganglionic plexus: [name]
- Patient follow-up: Electrophysiology Unit, HCUS.
- Analysis and publication of results: Electrophysiology Unit, HCUS.

11) *Response assessment:*

Six months after the start of the study, monitoring will be made of the results obtained up to that time, and a report will be presented if required. This same evaluation will be repeated at one year and after 24 months.

Calculation of sample size and statistical analysis

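### The only endpoint on pacemaker avoidance stops at 6 months although follow-up and the failure definition run to one year, and the handling of implants at withdrawal is not stated

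*Combined protocol and SAP*

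**What the plan says.** The Secondary objectives and section 8 (Measurements and interventions) both place the endpoint at 6 months: "Pacemaker-free survival in the cardiac neuroablation group at 6 months. This will be based on clinical follow-up of the recruited patients". The statistical analysis paragraph assigns it a Kaplan-Meier analysis but names no time point.

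Section 3 (Patient selection and withdrawal) defines two failures on ablation:
- "Therapeutic failure: in the cardiac neuroablation group, this is defined as the recurrence of syncope at one year"
- a separate procedural failure, meaning that denervation could not be completed and the atropine test stays positive

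It also gives two withdrawal criteria, each leading towards a pacemaker. One is "Syncope secondary to SND registered with electrocardiographic evidence. These patients will be offered pacemaker implantation". The other is inadequate denervation, of which it says: "In these cases, dual chamber pacemaker implantation will be indicated".

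Section 6 sets follow-up at one year from the intervention, and section 9 has visits at 1, 3, 6 and 12 months. Section 9 also puts a repeat atropine test, a Holter and the exercise test at month 6 for the ablation arm. The background cites a published series in which, among patients over 50, "only 13.6% of the patients in this subgroup required pacemaker implantation after 12 months".

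Syncope has its own secondary endpoint in section 8. Recurrence and syncope-free survival are headed 6 months, and the number of episodes per patient is compared at one year. All of this rests on clinical follow-up, with no ECG requirement.

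**The concern.** The rationale for the trial is that ablation might spare patients a permanent pacemaker, and the background says that solid long-term data are lacking. One endpoint addresses that directly, and as written it uses half of the planned follow-up.

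Three gaps follow:
- **Time point.** An implant after month 6 is not part of the stated endpoint, and an implant prompted by a month-6 test would come at or after the cut-off.
- **Unused definitions.** Therapeutic failure and failure of the procedure are defined, but no endpoint or analysis uses either. The reader will not be told what proportion of ablation patients were free of both at one year.
- **Event or censoring.** Both routes to a pacemaker named in section 3 are also withdrawal criteria. The plan does not say whether the patient then counts as an event or leaves the risk set.

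In addition, the recurrence criterion that leads to the offer of a pacemaker requires ECG evidence, while therapeutic failure does not. A patient can therefore be a therapeutic failure and remain event-free on this endpoint.

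**Working it through.** **Plan's own figure.** There is none to reproduce. No rate, precision or sample size is given for pacemaker-free survival. The 20 per arm was set for the SF-36 and is used here only as a denominator: 1/20 = 5 percentage points per patient.

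**Direction, without assumed rates.** Let S_PM(t) be the probability of being pacemaker-free at time t, and S_C(t) the probability of being free of the first of implantation, procedural failure or syncope recurrence.
1. A survival curve cannot rise, so S_PM(12) ≤ S_PM(6).
2. Every implantation is also a composite event, so S_C(12) ≤ S_PM(12).
3. Hence S_C(12) ≤ S_PM(12) ≤ S_PM(6).

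**Size, under assumptions.** The model is illustrative, with constant hazard over the year. Its inputs are assumed:
- r12, 12-month syncope recurrence: 7.8% to 30%. The low end is 100% − 92.2%, from the 18-month neurally mediated syncope series in the background. The 13.6% pacemaker rate serves as a mid-range value. Neither was measured as a 12-month recurrence rate.
- d, share of recurrences with ECG evidence, all assumed implanted: 25% to 100%.
- f, share with procedural failure, all assumed implanted at the start with no later syncope: 0% to 15%.

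Formulas:
- r6 = 1 − √(1 − r12)
- S_PM(6) = (1 − f)(1 − d·r6)
- S_PM(12) = (1 − f)(1 − d·r12)
- S_C(12) = (1 − f)(1 − r12)
- freedom from therapeutic failure alone at 12 months = 1 − (1 − f)·r12

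Effect of the 6-month cut alone, S_PM(6) − S_PM(12), with d = 100% and f = 0:

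| r12 | S_PM(6) | S_PM(12) | Gap |
|---|---|---|---|
| 7.8% | √0.922 = 96.0% | 92.2% | 3.8 points |
| 13.6% | √0.864 = 93.0% | 86.4% | 6.6 points |
| 30% | √0.70 = 83.7% | 70.0% | 13.7 points |

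The gap equals (1 − f)·d·(r12 − r6), so it shrinks when fewer recurrences lead to an implant. At r12 = 7.8%, d = 25% and f = 15% it is 0.85 × 0.25 × 3.8 = 0.8 points.

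S_PM(6) against the 12-month composite:
- smallest (r12 = 7.8%, d = 100%, f = 15%): 81.6% − 78.4% = 3.2 points
- largest (r12 = 30%, d = 25%, f = 0): 95.9% − 70.0% = 25.9 points, or 5.2 of 20 patients

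S_PM(6) against therapeutic failure alone, with f = 15%:
- r12 = 7.8%, d = 100%: 81.6% − 93.4% = −11.8 points
- r12 = 30%, d = 25%: 81.5% − 74.5% = +7.0 points

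Against that comparator the sign is not fixed.

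**Handling of withdrawal.** Suppose that 2 of 20 patients are procedural failures implanted at the start, 1 more is implanted later, and the other 17 are followed throughout. These counts are invented.
- all three are events: 17/20 = 85.0%
- the two early ones are censored at the start: 17/18 = 94.4%
- all three are censored at withdrawal: no event remains, and the curve stays at 100%

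The documents choose none of these.

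**The case against.** The strongest reply is that pacemaker-free survival and syncope recurrence are different questions. A patient without a pacemaker is correctly recorded as pacemaker-free. Recurrences go to the adjacent endpoint, which needs no ECG evidence, includes a one-year episode count, and has its own Kaplan-Meier curve with a log-rank test. Follow-up runs to 12 months and the Kaplan-Meier plan has no cut-off, so a 12-month estimate could be read off the planned data.

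Most of that stands, and it rules out several stronger readings that a reader might infer:
- **That ablation patients with undocumented syncope are counted as successes, or that this is the headline result.** The protocol uses neither label. The primary endpoint is the SF-36, and this is one of several secondary endpoints.
- **That the endpoint must overstate success against the one-year failure definition.** Inadequate denervation leads to a pacemaker without being therapeutic failure. It lowers pacemaker-free survival and can reverse the sign, as shown above.
- **That sparse Holter recording means most recurrences would lack ECG evidence.** Holter hours do not estimate that share. An ECG on admission may supply the evidence. The inclusion criteria also use the term for findings, such as chronotropic incompetence on exercise, that need not coincide with a faint.
- **That 13.6% is the trial's benchmark.** It is background from a subgroup of one series.

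The reply does not remove the core. A 12-month estimate that could be produced is not one that the plan commits to: both places that define the endpoint say 6 months. Syncope-free survival is also headed 6 months, and the one-year item is an episode count. Neither combines syncope with implantation or procedural failure. Section 3 defines the two failures separately and no composite, so the composite proposed here is a supportive addition and not a correction of something that the protocol promised.

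**Conclusion.** The point holds as a misalignment in a secondary endpoint. The only measure of pacemaker avoidance omits months 6 to 12, does not state whether implantation at withdrawal is an event, and leaves both failure definitions unused. The direction is certain in one respect: the 6-month figure can only equal or exceed both the 12-month figure and 12-month freedom from a composite that includes implantation.

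The size is not known. Under the assumed ranges, the gap to the composite is 3.2 to 25.9 points, and the time cut alone costs up to 13.7 points. These figures rest on a constant hazard and on recurrence, documentation and procedural-failure rates that the documents do not give. The unstated withdrawal rule could matter as much: in the invented example it moves the estimate from 85.0% to 94.4% or 100%.

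**What to change.** 1. In the Secondary objectives and section 8, set pacemaker-free survival in the ablation arm at 12 months from the procedure, with 6 months as a supporting time point. Give the same time points in the statistical analysis paragraph.
2. State that implantation at or after withdrawal, for either criterion in section 3, is an event and not a censoring. State also how a patient who is offered a device and declines it is handled in the analysis.
3. Add a supportive 12-month Kaplan-Meier analysis in the ablation arm. The event is the first of pacemaker implantation, failure of the procedure or syncope recurrence, as section 3 defines the last two. State the date assigned to a procedural failure, and report this curve beside pacemaker-free survival.
4. Reconcile the test schedule on which these dates depend. Section 9 states "Twenty-four hour Holter monitoring will be made at 2, 6 and 12 months in the cardiac neuroablation group", while the program of visits has the first Holter at month 1. Section 9 puts the repeat atropine test at 6 months, and the program lists it at month 1 only.

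The implantation criteria do not change. The cost is wording, with no extra visits or tests. The reported rate can only be equal or lower, and it needs the 12-month data. The timetable already places the analysis after 12 months of follow-up, so the final report need not be delayed.

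### The exercise-test secondary endpoint needs both arms at 6 months, but the visit list schedules that test only for the ablation arm and a 6-minute walk only for the pacemaker arm

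*Combined protocol and SAP*

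**What the plan says.** Five places in the protocol bear on this.

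- **Secondary objectives.** One objective is "Change in maximal heart rate and chronotropic incompetence in the exercise test".
- **Section 8, secondary endpoints.** The matching endpoint is "Differences in baseline and 6 months exercise test between the two groups".
- **Section 9, functional class assessment.** "The exercise test will be performed in both groups at 6 months".
- **Section 9, program of visits.** For the ablation arm: "Month 6: Face-to-face visit for 24-hour Holter monitoring, exercise test, SF-36 questionnaire and clinical follow-up". Its month-12 visit has neither test. For the pacemaker arm: "Month 6: Face-to-face visit for 6-minute walking test, SF-36 questionnaire, clinical follow-up, and interrogation of the device", and then "Month 12: Face-to-face visit for 6-minute walking test, SF-36 questionnaire, clinical follow-up, and interrogation of the device".
- **Statistical analysis of the variables.** A Student t-test is planned for the between-group difference in the 6-minute walk. No sentence deals specifically with the exercise test, although general rules for continuous and categorical variables are given.

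On baseline, section 1 (Study design) states: "Prior to inclusion in the study, all patients will undergo an electrocardiographic study, echocardiography, an atropine test, and a 6-minute walking test". The exercise test is not in that list.

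**The concern.** A between-group comparison needs the same measurement in both groups. The visit list gives each arm a different functional test after treatment, so a site working from it would collect the endpoint measure in one arm and an unlisted measure in the other. The one functional comparison that the analysis section names concerns the walk, which is not an endpoint and has no scheduled follow-up in the ablation arm.

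What is lost is more than precision. If one arm has no data, no analysis can recover the randomized comparison, and a month-6 or pre-treatment test that was not done cannot be obtained later.

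**Working it through.** There is no stated figure to reproduce and no power calculation is involved. The check sets the sections side by side and counts, using the planned 20 patients per arm (section 5 and the sample size paragraph), before any losses or the withdrawals described in section 3.

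**Step 1. Which test is listed in which arm and when**

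| Test and time | Ablation, visit list | Pacemaker, visit list | Sections 8 and 9 |
|---|---|---|---|
| Exercise test, month 6 | listed | not listed | both arms |
| 6-minute walk, month 6 | not listed | listed | not mentioned |
| 6-minute walk, month 12 | not listed | listed | not mentioned |

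**Step 2. Patients with data**

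- Exercise test at month 6 under the visit list: 20 + 0 = 20 of 40, all in the ablation arm.
- Exercise test at month 6 under section 9: 20 + 20 = 40 of 40.
- Walk at month 6 under the visit list: 0 + 20 = 20 of 40, all in the pacemaker arm. Month 12 is the same.

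Under the visit list, neither test has follow-up data in both arms. The only time at which both arms are listed for the walk is before inclusion, when there is no treatment effect to compare.

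**Step 3. Could the two names mean one test?** The conflict at month 6 would then disappear. The text points the other way. The visit list uses both names. The secondary objective ties the exercise test to maximal heart rate and chronotropic incompetence, and the inclusion criteria in section 3 use it to diagnose chronotropic incompetence. Section 1 names the walk as a separate pre-inclusion test.

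**Step 4. Is there a baseline exercise test?** The endpoint in section 8 requires one. The program of visits starts at month 1, and the pre-inclusion list in section 1 names only the walk. That list is not a complete baseline schedule: it also omits the SF-36, which section 8 needs before treatment ("The score obtained before the intervention will be compared with that recorded in the last year in both groups"). Its silence therefore does not prove that no baseline exercise test is intended. Eligibility does not fill the gap, because chronotropic incompetence is one of several alternative criteria and a patient can qualify on a pause, bradycardia or sinoatrial block alone. So section 8 implies a baseline test for every patient, and no section schedules it.

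**Step 5. Does one section take precedence?** No rule says so. Section 9 and the visit list also differ on two other ablation-arm tests. The repeat atropine test is placed after 6 months in one and at month 1 in the other, and the first Holter recording at month 2 in one and month 1 in the other. The mismatch on the exercise test is therefore not an isolated slip that a reader could resolve with confidence.

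**The case against.** The strongest reply is that the loss of data is conditional. Section 9 plainly commits both arms to the month-6 exercise test, the objectives and endpoints agree with it, and pacemaker patients already attend in person at month 6. On this view the visit list is an incomplete summary, and the case report form may well collect the test in both arms. This stands as a limit on what can be claimed: the contradiction is certain, the missing data are not. It does not remove the contradiction, because nothing tells staff which text to follow.

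A second reply is that the names were used loosely. No arm is listed for both tests in the visit list, section 9 introduces the exercise test under a functional-class heading that could also suit a walk, and the specific analysis sentence is about the walk. This reading is conceivable, but the references to maximal heart rate and chronotropic incompetence make it hard to sustain.

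A third reply is that the general t-test/Wilcoxon and Fisher/chi-squared rules already cover the exercise test. That is correct, and an absent analysis method is not part of this point. Those rules cannot supply measurements that one arm was never scheduled to have.

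Finally, the counts restate the schedule and do not measure bias or power. That is also fair. They show only that the comparison would have one empty arm.

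**Conclusion.** The concern holds. The endpoint and assessment text in sections 8 and 9 contradicts the program of visits, and the analysis section names a comparison of a test that is not an endpoint. If the visit list is followed, the month-6 exercise test is available for 20 of 20 ablation and 0 of 20 pacemaker patients, and the follow-up walk for 0 of 20 and 20 of 20. Neither post-treatment comparison can then be computed.

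The effect is confined to one secondary endpoint and one analysis sentence, and the SF-36 primary endpoint is untouched. The conclusion assumes that the exercise test and the walk are different tests, as the text indicates. The counts assume full recruitment with no losses or withdrawals. What is actually collected depends on the case report form, which is an annex not available here. The point should be corrected, but it does not threaten the main result.

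**What to change.** 1. List the exercise test at baseline and at month 6 in both arms, in section 1 and in the program of visits, so that they match sections 8 and 9.
2. Replace the walk-test sentence in the statistical analysis paragraph with the between-arm exercise-test comparison. Use the existing t-test/Wilcoxon rule for change in maximal heart rate and the existing Fisher/chi-squared rule for chronotropic incompetence.
3. In the same sentence, define chronotropic incompetence and say how paced rates in the pacemaker arm are counted. The documents do neither, and the control arm is programmed in a rate-responsive mode.
4. Either drop the follow-up walk or schedule it at the same visits in both arms.
5. Separately, reconcile section 9 and the visit list on the timing of the ablation-arm atropine test and first Holter recording. This review takes no position on which timing is right.

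The cost is wording in the visit list and section 1, and one analysis sentence. The additional tests are ones the protocol already commits to: the baseline exercise test through section 8 and the pacemaker-arm month-6 test through section 9. Dropping the pacemaker-arm follow-up walks would offset part of the work. Each change helps only patients who have not yet passed the visit concerned.
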